### **8.11. Occupational Exposure**

An occupational exposure occurs when, during the performance of job duties, a person (whether a healthcare professional or otherwise) gets in unplanned direct contact with the product, which may or may not lead to the occurrence of an AE.

An occupational exposure is reported to the drug safety unit within 24 hours of the investigator's awareness, using the SAE report form, regardless of whether there is an associated AE/SAE. Since the information does not pertain to a patient enrolled in the study, the information is not reported on a CRF; however, a copy of the completed SAE report form is maintained in the investigator site file.

### **8.12. Withdrawal Due to Adverse Events (See Also the Section on [Patient Withdrawal](#))**

Withdrawal due to AEs should be distinguished from withdrawal due to other causes, according to the definition of AE noted earlier, and recorded on the appropriate AE CRF page.

When a patient withdraws because of an SAE, the SAE must be reported in accordance with the reporting requirements defined below.

### **8.13. Eliciting Adverse Event Information**

The investigator is to report all directly observed AEs and all AEs spontaneously reported by the study patient/ legally acceptable representative. In addition, each study patient/ legally acceptable representative will be questioned about AEs.

### **8.14. Reporting Requirements**

Each AE is to be assessed to determine if it meets the criteria for SAEs. If an SAE occurs, expedited reporting will follow local and international regulations, as appropriate.

#### **8.14.1. Serious Adverse Event Reporting Requirements**

If an SAE occurs, Pfizer is to be notified within 24 hours of investigator awareness of the event.

In particular, if the SAE is fatal or life-threatening, notification to Pfizer must be made immediately, irrespective of the extent of available AE information. This time frame also applies to additional new information (follow-up) on previously forwarded SAE reports as well as to the initial and follow-up reporting of EDP, exposure via breastfeeding, and occupational exposure cases.

In the rare event that the investigator does not become aware of the occurrence of an SAE immediately (eg, if an outpatient study patient initially seeks treatment elsewhere), the investigator is to report the event within 24 hours after learning of it and document the time of his or her first awareness of the AE.

For all SAEs, the investigator is obligated to pursue and provide information to Pfizer in accordance with the time frames for reporting specified above. In addition, an investigator may be requested by Pfizer to obtain specific additional follow-up information in an expedited fashion. This information collected for SAEs is more detailed than that captured on the AE CRF. In general, this will include a description of the AE in sufficient detail to allow for a complete medical assessment of the case and independent determination of possible causality. Information on other possible causes of the event, such as concomitant medications, vaccines, and/or illnesses, must be provided. In the case of a patient death, a summary of available autopsy findings must be submitted as soon as possible to Pfizer or its designated representative.

#### **8.14.2. Non-serious Adverse Event Reporting Requirements**

All AEs will be reported on the AE page(s) of the CRF. It should be noted that the form for collection of SAE information is not the same as the AE CRF. Where the same data are collected, the forms must be completed in a consistent manner. For example, the same AE term should be used on both forms. AEs should be reported using concise medical terminology on the CRFs as well as on the form for collection of SAE information.

#### **8.14.3. Sponsor's Reporting Requirements to Regulatory Authorities**

AE reporting, including suspected unexpected serious adverse reactions, will be carried out in accordance with applicable local regulations.

### **9. DATA ANALYSIS/STATISTICAL METHODS**

Detailed methodology for summary and statistical analyses of the data collected in this trial will be documented in a Statistical Analysis Plan (SAP), which will be maintained by Pfizer. This document may modify the plans outlined in the protocol; however, any major modifications of the primary endpoint and/or its analysis will also be reflected in a protocol amendment.

This section describes the data analysis and statistical methods for this study.

## 9.1. Sample Size Determination

The study is designed to test the following hypotheses:

$$H_0: HR_{PFS}(A/B) \geq 1 \text{ versus } H_a: HR_{PFS}(A/B) < 1$$

Where  $HR_{PFS}(A/B)$  represents the hazard ratio (HR) for PFS in Arm A vs Arm B. A stratified log-rank test stratified by randomization stratification factors will be used for analysis of PFS.

Two hundred eighty-nine (289) PFS events will be required to have at least 90% power to detect a hazard ratio of 0.68 using a 1-sided log-rank test at a significance level of 0.025, and a 2-look group-sequential design with Lan-DeMets (O'Brien-Fleming)  $\alpha$ -spending function to determine the efficacy boundary and a Gamma Family (-7)  $\beta$ -spending function to determine the non-binding futility boundary.

The sample size of 640 patients for this study is determined based on the assumptions that the median PFS for patients in Arm B is 33 months and that combination treatment including avelumab (Arm A) is expected to increase the median PFS to  $\geq 48.5$  months, corresponding to a HR of  $\leq 0.68$  under the exponential model assumption.

The sample size further assumes a 15% drop-out rate within each treatment arm and a non-uniform patient accrual over a 22-month period. The data cutoff for the primary PFS analysis will occur after the target number of events has been reached and the last patient randomized in the study has been followed for at least 24 months after randomization.

The sample size of 640 patients will also allow the assessment of a difference in OS. OS will be tested using a hierarchical testing procedure, provided the primary endpoint, PFS, is statistically significant favoring Arm A. A total of 392 OS events will be required to have 80% power to detect a HR of 0.75 using a 1-sided log-rank test at a significance level of 0.025 and a 5-look group sequential design with Lan-DeMets (O'Brien-Fleming)  $\alpha$ -spending function to determine the efficacy boundary. It is assumed that the median OS for patients in Arm B is 70 months, and that treatment with avelumab (Arm A) is expected to increase the median OS to  $\geq 93$  months, corresponding to a HR of  $\leq 0.75$  under the exponential model assumption. The sample size further assumes a 5% drop-out rate for OS in each treatment arm, and a follow-up of approximately 106 months after the last patient is randomized. The data cutoff for the final OS analysis will occur after the target number of deaths has been reached in the study.

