OS will be compared between the 2 treatment arms using a hierarchical testing procedure, provided the primary endpoint, PFS, is statistically significant favoring Arm A. A maximum of 5 analyses are planned for OS: at the time of the interim analysis for PFS, at the time of the final analysis for PFS, after 270 deaths are observed, after 345 deaths are observed, and a final analysis for OS after 392 deaths are observed. An  $\alpha$ -spending function according to Lan-DeMets (O'Brien-Fleming) independent of the one used for the primary efficacy analysis will be used to preserve the 0.025 overall level of significance across the two hypotheses and the repeated testing of the OS hypotheses in the interim and the final analyses. The trial allows for the stopping of the study for a superior OS result, provided the

primary endpoint, PFS, has already been shown to be statistically significant favoring Arm A.

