With 392 deaths, the study will have 80% cumulative power (unadjusted for the pre-testing, in the hierarchical procedure, of PFS) to detect a hazard ratio of 0.75 using a 1-sided log-rank test at a significance level of 0.025 and a 5-look group-sequential design with Lan-DeMets (O’Brien-Fleming)  $\alpha$ -spending function to determine the efficacy boundary. If the median OS in Arm B is 70 months (Ang KK, et al., 2010^2; Ang KK, et al., 2014), a hazard ratio of 0.75 corresponds to an increase in median OS from 70 months in Arm B to 93 months in Arm A under the exponential model assumption.

Table 6 summarizes the power to detect several hazard ratios and the estimated duration of the study based on the same number of patients that are planned to be enrolled in the study to meet the primary endpoint and assuming a 5% dropout rate for survival follow-up. These calculations are conditional on achieving statistical significance for the test of PFS.

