**Table 7. Simulated cumulative probabilities to stop for futility at the interim or final PFS analysis**

Scenario	Look	Number of PFS events	Calendar Time (months)	P(Reject H 01 )	P(Reject H a1 )
H 01 is true (HR=1)	Interim	217	34	0.0093	0.7679
	Final	289	44	0.0246	0.9754
H a1 is true (HR=0.68)	Interim	217	38	0.6917	0.0197
	Final	289	51	0.9010	0.0990

Simulations performed in EAST 6.4.1 with number of simulations = 10,000 and seed=7282016.

The secondary OS endpoint will be analyzed using a hierarchical testing procedure, provided the primary endpoint PFS endpoint is statistically significant favoring Arm A. An  $\alpha$ -spending function according to Lan-DeMets (O'Brien-Fleming) independent of the one used for the primary efficacy analysis will be used to preserve the 0.025 overall level of significance across the hypotheses and the repeated testing of the OS hypotheses in the interim and final analyses. The trial allows for the stopping of the study for a superior OS result, provided the primary PFS endpoint has already been shown to be statistically significant favoring Arm A.

A maximum of five analyses are planned for OS:

- 1) an interim analysis at the time of the interim analysis for PFS (provided PFS is significant);
- 2) an interim analysis at the projected time of the final analysis for PFS (provided PFS is significant);
- 3) an interim analysis when 270 deaths are observed;
- 4) an interim analysis when 345 deaths are observed;
- 5) a final analysis for OS when 392 deaths are observed.

The exact nominal p-values that will need to be observed to declare statistical significance at the time of these analyses for OS will depend on the number of OS events that have been observed at the time of these analyses and the  $\alpha$  for OS already spent at the time of earlier analyses.

If OS is tested alone, independent of the testing strategy for PFS, the design concerning overall survival analyses will have the following operating characteristics. These calculations are unadjusted for the pre-testing of PFS.

**Table 8. Simulated cumulative probabilities to stop for efficacy on overall survival at PFS interim analysis, final PFS analysis, third interim OS analysis, fourth interim OS analysis, or final OS analysis**

Scenario	Look	Number of deaths	Calendar Time (months)	P(Reject $H_{0j}$ )
$H_{02}$ is true (HR=1)	Interim PFS	139	38	<0.0001
	Final PFS	198	51	0.0005
	3 rd Interim OS	270	69	0.0067

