	4 th Interim OS	345	93	0.0160
	Final OS	392	112	0.0247
$H_{a2}$ is true (HR=0.75)	Interim PFS	122	38	0.0104
	Final PFS	176	51	0.1060
	3 rd Interim OS	270	78	0.4613
	4 th Interim OS	345	106	0.6973
	Final OS	392	127	0.8015
$H_{a2}$ is true (HR=0.80)	Interim PFS	126	38	0.0037
	Final PFS	181	51	0.0470
	3 rd Interim OS	270	76	0.2625
	4 th Interim OS	345	103	0.4738
	Final OS	392	124	0.5825

Interim and final PFS analyses calendar time expected at 38 and 51 months, respectively, under  $H_{a1}$  (HR for PFS=0.68).

Simulations performed in EAST 6.4.1 with number of simulations = 10,000 and randomization seed =7282016.

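### The stated 80% OS power is that of OS tested alone; Protocol 9.1 does not say so, and SAP 5.1.1 wrongly calls the same figures in Table 6 conditional on PFS success

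*Protocol*

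**What the plan says.** Protocol 9.1 first sets the gate: "OS will be tested using a hierarchical testing procedure, provided the primary endpoint, PFS, is statistically significant favoring Arm A". The next sentence gives the power: "A total of 392 OS events will be required to have 80% power to detect a HR of 0.75". The test behind that figure is a one-sided log-rank at 0.025 with five group-sequential looks. The section does not say whether the 80% allows for the gate. Protocol 9.6 places the five OS looks at the PFS interim, at the PFS final analysis, and then "after 270 deaths are observed, after 345 deaths are observed, and a final analysis for OS after 392 deaths are observed".

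The SAP describes this power in three places:

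- SAP 5.1.1, main text, 392 deaths at hazard ratio 0.75: "80% cumulative power (unadjusted for the pre-testing, in the hierarchical procedure, of PFS".
- SAP 5.1.1, text introducing Table 6 (80%, 58% and 93% at hazard ratios 0.75, 0.80 and 0.70): "These calculations are conditional on achieving statistical significance for the test of PFS".
- SAP 5.1.2, text introducing Table 8 (final cumulative power 0.8015 at 0.75 and 0.5825 at 0.80), which describes OS as tested on its own: "These calculations are unadjusted for the pre-testing of PFS".

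Neither document gives a probability that PFS and OS both succeed, or a correlation between the two tests.

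**The concern.** Three different quantities can be called OS power in a hierarchical design:

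- **Marginal:** OS crosses its boundary, with PFS ignored.
- **Conditional:** OS crosses, given that PFS succeeded.
- **Gated:** PFS and OS both succeed, which is what an OS claim requires here.

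Marginal and conditional power are equal only if the two test statistics are independent. Deaths from any cause are PFS events (Protocol 9.3.1), so the endpoints share events and a positive correlation is expected. Gated power is then below marginal power, and conditional power is above it.

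A Protocol reader who sees the gate followed at once by 80% may take 80% as the chance of an OS claim under the design assumptions. A SAP reader is told within one section that the same number is both unadjusted and conditional. What is at stake is how the prospects for the only formally tested secondary endpoint are read; its final analysis is projected at 127 months (SAP Table 6). The validity of the test is not at stake.

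**Working it through.** **Inputs.**
- OS: 392 deaths, hazard ratio 0.75, 1-sided 0.025, five looks, Lan-DeMets O'Brien-Fleming spending (Protocol 9.1). Looks at 122, 176, 270, 345 and 392 deaths (SAP Table 8, hazard ratio 0.75). For the first two, the note to Table 8 gives: "Interim and final PFS analyses calendar time expected at 38 and 51 months, respectively".
- PFS: 217 and 289 events, hazard ratio 0.68, interim efficacy bound 2.338, futility bound 0.728 (Protocol 9.6). Cumulative power 0.9010 (SAP Table 7).
- Allocation 1:1.

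**Step 1: reproduce the 80%.** For a fixed design, power = Φ(√(d/4)·|ln HR| − 1.960) = Φ(√98 × 0.2877 − 1.960) = Φ(0.888) = 81.3%. With five looks the spending function gives bounds of about 3.85, 3.16, 2.48, 2.18 and 2.06, and power falls to **80.1%**. The stated values are 80% and 0.8015, so the figure reproduces as marginal power.

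**Step 2: identify what Table 6 holds.** Marginal five-look power, recomputed:

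| OS hazard ratio | Recomputed marginal | SAP Table 6 | SAP Table 8 |
|---|---|---|---|
| 0.75 | 80.1% | 80% | 0.8015 |
| 0.80 | 58.4% | 58% | 0.5825 |
| 0.70 | 93.6% | 93% | not listed |

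Tables 6 and 8 also cite the same software version, number of simulations and seed. Table 6 therefore holds marginal values.

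**Step 3: PFS power.** The bounds are 2.338 and 2.012, with 0.0097 of alpha spent at the interim. Power is 90.1%, which matches Table 7.

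**Step 4: gated and conditional power.** If the statistics are independent, gated power = 0.901 × 0.801 = 0.72. For other cases the PFS and OS statistics were drawn jointly (multivariate normal, 2,000,000 draws). The PFS futility bound was applied, and an OS crossing counted only at or after the look at which PFS succeeded. The correlation is an assumption.

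| Assumed PFS–OS correlation | Gated (both succeed) | Conditional on PFS success |
|---|---|---|
| 0 | 72.1% | 80.1% |
| 0.3 | 73.9% | 82.1% |
| 0.4 | 74.6% | 82.8% |
| 0.5 | 75.3% | 83.7% |
| 0.6 | 76.2% | 84.6% |

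Conditional is gated divided by PFS power; at 0.5, 0.753/0.901 = 0.84. Leaving out the futility rule moves gated power by about 0.1 point.

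**Step 5: patient-level cross-check.** This used 640 patients, exponential medians of 33 and 48.5 months (PFS) and 70 and 93 months (OS), and 8,000 runs per model. Three inputs had to be assumed: ramp-up accrual over 22 months (the Protocol says only that accrual is non-uniform), 15% PFS dropout by 51 months and 5% OS dropout by 127 months (no time basis is stated). OS boundaries were rounded.
- Progression independent of death within arm: final-statistic correlation 0.42, gated power 74.7% (standard error 0.5 points), conditional 83.0%.
- PFS and OS perfectly ordered, an extreme: gated 78.2%, conditional 87.0%.

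**Step 6: bounds.** Gated power cannot exceed the marginal 80%. A value below 72% would need a negative correlation, which shared deaths make implausible.

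**The case against.** The strongest reply is that the plan contains no error of calculation and hides nothing. The 80% is correct for what SAP 5.1.1 says it measures, and SAP 5.1.2 says plainly that Table 8 treats OS in isolation. The Protocol sentence ties the 80% to the OS log-rank test and its five looks; it does not claim gated power. The Protocol also leaves detailed methodology to the SAP (Protocol 9). Marginal power for a gated secondary endpoint is an acceptable thing to report when it is labelled. All of this stands, and a reader who inferred that the plan as a whole ignores the gate would be wrong.

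The Table 6 sentence can also be read procedurally: the figures apply once the gate has been passed. On that reading both SAP labels warn that the risk of PFS failure is left out. Nor does the label flatter the design, because true conditional power would be above 80%. That limits the harm, but does not rescue the wording. Conditional on significance has a definite meaning, and the same numbers carry a different label for Table 8.

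The reply does not supply the missing qualification in Protocol 9.1, or a gated figure in either document.

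**Conclusion.** The point holds as a matter of labelling and a missing figure. The 80% is marginal OS power. Protocol 9.1 should say so, and the sentence on Table 6 is wrong.

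Gated power is lower than 80% by an amount that depends on an unstated correlation. The shortfall is 80.1 − 72.1 = 8.0 points if the statistics are independent, 80.1 − 74.6 = 5.5 points at 0.4 and 80.1 − 76.2 = 3.9 points at 0.6. It would be smaller with stronger dependence.

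A reader might infer that the design delivers 75% under its own assumptions, or that OS power is overstated by exactly 5 points. The documents do not support a single value: they give no PFS–OS dependence, no accrual shape and no time basis for dropout. About 75% is a reasonable central value under an assumed correlation of 0.4–0.5, and should be shown only within the range from 72% to the 80% ceiling. Nor does this finding bear on type I error control.

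**What to change.** 1. Protocol 9.1: state that the 80% is the power of OS tested alone, without allowance for the PFS gate.
2. SAP 5.1.1: replace the sentence calling the Table 6 calculations conditional with the unadjusted description already used for Table 8.
3. Both places: add the gated OS power as a range, with the assumed correlation beside each value (72% at zero, about 75–76% at 0.4–0.6, ceiling 80%), preferably from the sponsor's own joint simulation with its accrual and dropout inputs stated.

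The cost is a few sentences and one simulation. The 392 deaths, 640 patients, look schedule, boundaries and decision rules stay as they are. The only downside is that a less favourable figure appears beside the 80%.

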## 9.2. Analysis Populations

### 9.2.1. Full Analysis Set

The full analysis set (FAS) will include all patients who are randomized. Patients will be classified according to the treatment assigned at randomization. The FAS will be the primary population for evaluating all efficacy endpoints and patient characteristics.

### **9.2.2. Per-Protocol Analysis Set**

The per-protocol analysis set is a subset of the FAS and will include patients who do not meet criteria that could impact the key objectives of the study. These criteria will be pre-specified in the statistical analysis plan. The per-protocol analysis set will be used for sensitivity analyses of the primary efficacy endpoint, PFS.

### **9.2.3. Safety Analysis Set**

The safety analysis set will include all patients who receive any study treatment. Patients will be classified according to the treatment assigned at randomization unless the incorrect treatment(s) are received throughout the treatment period, in which case patients will be classified according to the first treatment received. The safety analysis set will be the primary population for evaluating treatment administration/compliance and safety.

### **9.2.4. Pharmacokinetics Analysis Set**

The PK concentration analysis set is a subset of the safety analysis set and will include patients who have at least 1 concentration above the lower limit of quantitation (LLQ) for avelumab or cisplatin (total and free).

The PK parameter analysis set is a subset of the safety analysis set and will include patients who have at least 1 of the PK parameters of interest for avelumab or cisplatin.

### **9.2.5. Immunogenicity Analysis Set**

The immunogenicity analysis set is a subset of the safety analysis set and will include patients who have at least 1 ADA/Nab sample collected for avelumab in Arm A.

### **9.2.6. Biomarker Analysis Set**

The biomarker analysis set is a subset of the safety analysis set and will include patients who have at least 1 screening biomarker assessment. Analysis sets will be defined separately for blood-based and tumor tissue-based biomarkers.

## **9.3. Efficacy Analysis**

All analyses will be performed on the FAS unless otherwise specified.

All analyses will be performed by using SAS® Version 9.1.3 or higher.

### **9.3.1. Analysis of the Primary Endpoint**

PFS is defined as the time from the date of randomization to the date of the first documentation of objective PD per modified RECIST v1.1 or death due to any cause, whichever occurs first.

The following will be considered events in the analysis of PFS:

- Death due to any cause;

- Locoregional disease progression per RECIST v1.1 which is subsequently confirmed by pathology;
- Locoregional clinically detectable progression that is confirmed by pathology;
- Surgical removal (salvage) of primary tumor with tumor present on final pathology;
- Salvage neck dissection >20 weeks (140 days) after completion of SOC CRT with tumor present on final pathology;
- Metastatic (distant metastases) disease progression per RECIST v1.1.

For the primary analysis, PFS data will be censored on the date of the last adequate tumor assessment for patients who do not have an event (PD per modified RECIST v1.1 or death); the analysis will consider any PD per modified RECIST v1.1 or death as an event regardless of the number of prior missing tumor assessments or timing of the event with respect to initiation of anti-cancer therapy.

The primary analysis of PFS will be performed based on the FAS. A stratified log-rank test (1-sided) stratified by randomization stratification factors will be used at the interim and/or final analyses with the overall significance level preserved at 0.025 (1-sided). PFS times associated with each treatment arm will be summarized using the Kaplan-Meier method and displayed graphically where appropriate. CIs for the 25th, 50th, and 75th percentiles will be reported. The stratified Cox proportional hazards model will be fitted to compute the treatment hazard ratio and the corresponding 95% CI.

A sensitivity analysis for PFS will be performed using the methodology outlined for the primary analysis of PFS above but defining PD as per standard RECIST v1.1. Summary of discordance of PD (event and timing) as well as reasons for discordance between assessment of PFS per modified RECIST v1.1 and standard RECIST v1.1 will be provided for each treatment arm.

PFS based on modified RECIST v1.1 will also be evaluated based on the per-protocol analysis set as a sensitivity analysis using the methodology outlined for the primary analysis of PFS.

Other sensitivity analyses will be pre-specified in the SAP.

